4. SUBJECT POPULATIONS

4.1 Randomized Population

The randomized population consists of all subjects who are randomized at Visit 2 to one of the five treatment groups: JTE-051 50 mg QD, 100 mg QD, 150 mg QD, 200 mg QD and placebo QD.

4.2 Safety Population

Safety population consists of the randomized subjects who receive at least one dose of JTE-051 or placebo after the randomization, including those who did not complete the study.

4.3 Intent-To-Treat (ITT) Population

The Intent-To-Treat (ITT) population consists of the randomized subjects who receive at least one dose of the study drug and have at least one post-baseline efficacy assessment during the DB treatment period.

4.4 Per Protocol (PP) Population

The Per Protocol (PP) population is a subset of the ITT population in which subjects do not incur any of the major protocol deviations below.

Major protocol deviation criteria:

1. Dosing compliance not in 80-120% (based on actual dosing period)
2. Subject's last dose not between Days 68-100
3. Subject did not take 272-400 tablets in total
4. >4 days between last dose and last non-follow-up efficacy assessment
5. Not meeting Inclusion Criterion #3 or #4
6. Not meeting Exclusion Criterion #1, #2 or #28
7. Subject took "key" prohibited concomitant medications or had unstable background therapy that could potentially affect efficacy results/interpretation
8. Subject took incorrect study medication, e.g. due to incorrect drug dispense
9. Significant procedural deviations/non-compliance that could potentially affect efficacy results/interpretation

A pre-analysis meeting will take place after all data have been entered into the database and cleaned, but before the release of the randomization code, to identify the PP population. The decisions made to select the PP population will be documented.

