3.3.2. Exclusion Criteria

The following criteria will exclude a subject from participating in the study:

1. Prior/current exposure to biologic and/or kinase inhibitor therapy;
2. Does not meet all study restrictions, including previous/concomitant medication restriction criteria, as described in Section 3.5.4 of the protocol;
3. White blood cell count of $<3.0 \times 10^9/\text{L}$ ($<3000/\text{mm}^3$), absolute neutrophil count of $<1.5 \times 10^9/\text{L}$ ($<1500/\text{mm}^3$) or absolute lymphocyte count $<0.8 \times 10^9/\text{L}$ ($<800/\text{mm}^3$) at the Screening Visit (Visit 1);
4. Hemoglobin $<9 \text{ g/dL}$ or platelet count $<100,000/\text{mm}^3$ at the Screening Visit (Visit 1);
5. Alanine aminotransferase (ALT) $>1.2 \times$ the ULN; aspartate aminotransferase (AST) $>1.2 \times$ the ULN or total bilirubin $>1.5 \times$ the ULN at the Screening Visit (Visit 1);

6. Clinical evidence of renal impairment or an estimated glomerular filtration rate (eGFR) ≤ 60 mL/min/1.73m² at the Screening Visit (Visit 1), using the abbreviated Modification of Diet in Renal Disease (MDRD) equation;

7. Serum triglycerides >400 mg/dL at the Screening Visit (Visit 1);

8. Positive viral serology at the Screening Visit (Visit 1) for:

- Human immunodeficiency virus: positive HIV antibodies (Ab)
- Hepatitis B virus: positive total hepatitis B core (HBc) Ab or positive hepatitis B surface antigen (HBsAg) or
- Hepatitis C virus (HCV): positive HCV Ab;

9. Positive drug of abuse and alcohol test results at the Screening Visit (Visit 1);

Note: Adequate (i.e., non-abusive) use of prescription drugs, according to the Investigator's judgment is permitted, provided that the concomitant medications restrictions required by the protocol are met. Positive test results for cannabinoids will result in exclusion of subject from the study.

10. History or presence of substance abuse, drug addiction or alcoholism within 1 year prior to the Screening Visit (Visit 1);

[figure not shown]
11. Positive Purified Protein Derivative (PPD) or quantiFERON[®]-TB Gold-In-Tube test (**Note:** either test can be performed, according to the local guidelines), positive chest radiography findings for tuberculosis or any other evidence of tuberculosis;

- For subjects with a history of Bacille Calmette-Guérin (BCG) vaccination the quantiFERON[®]-TB Gold-In-Tube test should be performed;

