6.4 Efficacy Analysis

Analyses of primary and secondary efficacy parameters will be performed for both the ITT and PP populations, respectively.

For efficacy analyses, the DB treatment period is defined as the time period from the first dose of study drug to the last dose of study drug plus 4 days. The end of treatment (EOT) value is defined as the last value taken during the DB treatment period.

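### SAP 4.4, per-protocol criterion 6 is worded with reversed polarity: read literally, it flags the eligible subjects

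*SAP*

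**What the plan says.** SAP 4.4 defines the PP population as a "subset of the ITT population in which subjects do not incur any of the major protocol deviations below" and lists nine deviations. Two of them concern eligibility. Criterion 5 is "Not meeting Inclusion Criterion #3 or #4". Criterion 6 is "Not meeting Exclusion Criterion #1, #2 or #28".

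Protocol 3.3.2 opens its list with "The following criteria will exclude a subject from participating in the study". Exclusion 1 is prior or current exposure to a biologic or kinase inhibitor. Exclusion 2 is failure to satisfy the study restrictions, including those on medication. The text of exclusion 28 is not shown in the public protocol. That is not a fault in the plan, and the point does not need it.

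Three further criteria in SAP 4.4 concern exposure. Criterion 1 requires 80-120% compliance over the actual dosing period. Criterion 2 is "Subject's last dose not between Days 68-100". Criterion 3 is "Subject did not take 272-400 tablets in total".

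On use of the set, SAP 6.4 states: "Analyses of primary and secondary efficacy parameters will be performed for both the ITT and PP populations, respectively". SAP 4.4 also provides for a meeting, after data cleaning and before the randomization code is released, at which the PP set is identified and the decisions are documented.

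**The concern.** Not meeting an inclusion criterion makes a subject ineligible, so criterion 5 is correct. Criterion 6 applies the same phrase to exclusion criteria, where it has the opposite effect.

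What is at stake is whether the PP set can be programmed from the SAP alone. Protocol 3.8.3 repeats the primary analysis on the PP set only if that set drops 20% or more of the ITT subjects. SAP 6.4 has no such condition and covers the secondary parameters too, and SAP 5.1 and 6.3 add PP tables of demographics and baseline characteristics. If criterion 6 cannot be followed as written, the meeting must depart from the written rule to reach a sensible set, and pre-specification is meant to make that unnecessary.

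**Working it through.** **Criterion 6.** No arithmetic applies, so the check is to apply the wording to two subjects. Subject A is fully eligible and meets none of exclusions 1, 2 and 28. Subject B had a prior biologic and meets exclusion 1 only. The literal text can be taken in two ways: the subject meets none of the three, or the subject fails to meet at least one of them.

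| Reading | A flagged? | B flagged? |
|---|---|---|
| Purpose of the rule | No | Yes |
| Literal: meets none of the three | Yes | No |
| Literal: fails to meet at least one | Yes | Yes (clear of 2 and 28) |
| With 'Not' deleted | No | Yes |

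Under either literal reading the eligible subject A is flagged. Under the first, the ineligible subject B is also kept. Only the corrected wording matches the purpose.

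Exclusion 2 adds a second negative. A subject meets it by failing the study restrictions. Not meeting it therefore means complying with them, and criterion 6 as written lists that as a deviation.

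**Criterion 3, as a side check.** Inputs: 4 tablets daily for 12 weeks (Protocol 3.7.5), and the limits in SAP 4.4. Assumption: treatment duration D equals the day of the last dose.

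- The tablet limits are the day limits times four: 4 x 68 = 272 and 4 x 100 = 400.
- The planned total is 4 x 84 = 336 tablets. 272/336 = 81.0% and 400/336 = 119.0%, so the limits are also close to 80-120% of planned exposure.
- Criteria 1 and 3 together give a compliance window from max(80%, 272/(4D)) to min(120%, 400/(4D)).

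| Last dose | 272/(4D) | 400/(4D) | Effective window |
|---|---|---|---|
| Day 68 | 100.0% | 147.1% | 100-120% |
| Day 84 | 81.0% | 119.0% | 81.0-119.0% |
| Day 100 | 68.0% | 100.0% | 80-100% |

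For a subject who finishes on schedule, Visit 6 is Day 84 ± 2 and the last dose is the day before, so D is 81 to 85. The floor then runs from 272/324 = 84.0% down to 272/340 = 80.0%, and the ceiling is between 120% and 400/340 = 117.6%.

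Each of the three criteria removes someone whom the other two keep:

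- Criterion 1: Day 100 with 280 tablets (280/400 = 70%).
- Criterion 2: Day 60 with 276 tablets (276/240 = 115%).
- Criterion 3: Day 68 with 268 tablets (268/272 = 98.5%).

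**The case against.** The strongest reply is that the trial's own usage treats meeting the criteria as being eligible. Withdrawal reason 4 in Protocol 3.4 uses failure to meet the inclusion/exclusion criteria to mean ineligibility. The note on Sjögren's syndrome in 3.3.2, and the one on occasional analgesic use in 3.5.4.1, speak in the same way of all other criteria being met. On that usage, criterion 6 says what was intended. Criterion 5 is parallel, and a PP set emptied of eligible subjects could not pass unnoticed at the blinded meeting.

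Most of this stands. It shows that the intent is recoverable. A reader might infer from the literal text that the PP set will in fact be emptied; the documents do not support that as a realistic outcome. What the reply does not do is make the line correct. The protocol phrases are collective and cover both kinds of criteria at once. The SAP gives the exclusion criteria a line of their own, where the ordinary meaning is the opposite.

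It can also be said that the consequence is limited, because the PP analyses run beside the ITT analyses. That is true, and it limits the weight of the point without removing it.

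**Conclusion.** Criterion 6 is reversed as written and should be corrected. This is a wording error. Coded literally, it would flag every eligible subject; read as intended, it changes nothing. No number of wrongly excluded subjects can be given, and in practice none is expected if the meeting applies the intent. The conclusion rests only on Protocol 3.3.2's meaning of an exclusion criterion.

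A reader might also infer that criterion 3 overrides criteria 1 and 2, or departs from an intended PP set, and should be deleted. The documents do not support this. The SAP states no intended set apart from its list, joint limits are not contradictory in themselves, and each criterion still does work of its own. A limit on total tablets is coherent beside a limit on relative compliance. Without criterion 3, a subject with a last dose on Day 68 and 80% compliance would pass the exposure rules on 0.80 x 272 = 217.6 tablets, or 217.6/336 = 65% of planned exposure. What remains is that the SAP does not say how the three limits are meant to combine, and that the effect is small for subjects who finish on schedule.

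**What to change.** Delete 'Not' from criterion 6, so that meeting exclusion criterion 1, 2 or 28 is the deviation, before the blinded pre-analysis meeting. The cost is one word of SAP text. There is no downside, and ITT results do not change.

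Optionally, add one sentence confirming that criterion 3 is meant as a total-exposure rule applied together with criteria 1 and 2. No change to its limits is proposed.

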4.5 Pharmacokinetic (PK) Population

The PK population consists of the randomized subjects who receive at least one dose of JTE-051 and have at least one usable JTE-051 plasma concentration measurement.

5. ANALYSIS PARAMETERS

5.1 Demographic and Baseline Characteristics

Demographic variables include age, gender, ethnic group, geographical region, race, body weight, height and body mass index (BMI).

Baseline (last non-missing value prior to first dose) subject characteristics include the following parameters: duration (years) of active RA, tender/painful joint counts (68 and 28), swollen joint counts (66 and 28), subject's assessment of arthritis pain, subject's global assessment (SGA) of disease activity, physician's global assessment of disease activity (PGA), Health Assessment Questionnaire Disability Index (HAQ-DI), hs-CRP, Disease Activity Score 28 with CRP (DAS28-CRP), Simple Disease Activity Index (SDAI), Clinical Disease Activity Index (CDAI), Rheumatoid Factor (RF), Methotrexate (MTX) dose, Concomitant Steroids, % positive anti-CCP antibody and % patients who took DMARDs (i.e., Sulfasalazine, Hydroxychloroquine or Chloroquine). In addition, hs-CRP at screening will be summarized. Where both screening and screening re-test values are available, the screening re-test value will be used in the summary.

Summary tables for demographic and baseline characteristics will be generated for randomized, safety, ITT and PP populations, respectively.

5.2 Efficacy Parameters

5.2.1 Primary Efficacy Parameter

[figure not shown]
The primary efficacy parameter is the ACR20 response rate at end of treatment (EOT), defined as percentage of subjects achieving at least 20% improvement from baseline in tender and swollen joint counts and at least 20% improvement from baseline in 3 of the 5 remaining ACR core set measures.

[figure not shown]
5.2.2 Secondary Efficacy Parameters

The secondary efficacy parameters (evaluated at Weeks 2, 4, 8, 12, 16 and EOT, respectively, unless otherwise stated):

- Percentage of subjects achieving ACR20/50/70 response rate (except ACR20 at EOT which is the primary parameter)
- Change from baseline in SDAI
- Percentage of subjects who achieved remission based on SDAI (≤ 3.3)
- Percentage of subjects who achieved low disease activity based on SDAI (≤ 11)
- Change from baseline in CDAI
- Percentage of subjects who achieved remission based on CDAI (≤ 2.8)
- Percentage of subjects who achieved low disease activity based on CDAI (≤ 10)
- Percentage of subjects achieving Boolean Remission
- Change from baseline in DAS28-CRP
- Percentage of subjects with DAS28-CRP of <2.6
- Percentage of subjects with DAS28-CRP of <3.2

- Percentage of subjects with good European League Against Rheumatism (EULAR) response at Week 12
- Percentage of subjects with moderate EULAR response at Week 12
- The lowest percentage change from baseline of 3 measures: tender joint count, swollen joint count and median change of the remaining 5 core measures (numeric ACR [ACR-N] index)
- Change from baseline in the Health Assessment Questionnaire Disability Index (HAQ-DI)
- Change from baseline in the number of tender and swollen joint counts (68/66 joints will be counted)
- Change from baseline in subject pain score by numeric rating scale (NRS)
- Change from baseline in subject global assessment (SGA) of disease activity by NRS
- Change from baseline in physician global assessment (PGA) of disease activity by NRS
- Change from baseline in hs-CRP

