5.2.5.7 EULAR Response Criteria

The EULAR response criteria will be assessed by the Sponsor.

This parameter considers both the change in DAS28 between two time points, as well as DAS28 value at a specific time point.

DAS28-CRP will be utilized in calculating the EULAR response in the study subjects.

DAS28 improvement →			
Present DAS28 ↓	>1.2	>0.6 and ≤ 1.2	≤ 0.6
≤ 3.2	good response	moderate response	no response
>3.2 and ≤ 5.1	moderate response	moderate response	no response
>5.1	moderate response	no response	no response

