6.1 Sample Size

Approximately 250 eligible subjects (50 in each treatment group) are randomized into the DB treatment period of this study.

The primary efficacy evaluation will be to compare the ACR20 response rate between JTE-051 with placebo at EOT. From one study comparing mavrilimumab with placebo in combination with stable MTX, the ACR20 of mavrilimumab and placebo at Week 12 were 0.69 and 0.40, respectively. Assuming the ACR20 of at least one of the JTE-051 doses to be at least 0.30 above placebo, the following sample size per group will be needed to detect a statistical significant difference at the 5% level with about 80% power (using 2-sided Fisher's exact test):

Placebo ACR20	0.25	0.35	0.45
Sample size per group	47	48	47

About 50 randomized subjects per group would therefore give at least an 80% power for a range of placebo responses. The sample size calculation was carried out using the software SiZ 6.2 (Cytel Inc., 2013).

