6.4.2 Analyses of Secondary Efficacy Endpoints

For dichotomous secondary efficacy parameters, similar analyses as the primary efficacy parameter will be used by time point, i.e., the Fisher's exact test for pairwise comparisons with placebo and the Cochran-Armitage test for trend.

For continuous efficacy parameters, the mixed model with fixed effects for treatment, time, treatment by time interaction, the stratification factors and the baseline, and measurements within each subject as repeated measures will be used.

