6.4.3 Supportive Analyses of Efficacy Parameters

For dichotomous efficacy parameter analysis with multiple time points, a supportive analysis will be performed using a generalized estimating equation (GEE) method on the logit scale. The model includes effects for treatment, time, treatment by time interaction, stratification factors and subject as the repeated factor. The odds ratio (OR) of each JTE-051 dose group relative to placebo at the same time point will be estimated.

Model: (generalized estimating equation (GEE) method on the logit scale)

```
proc genmod data=xxxx;
  class usubjid trtn(ref=1) region(ref=0) hscrpn(ref=0);
  model SAEP=trtn time trtn*time regionn hscrpn;
  repeated subject=usubjid/type=un corrw;
run;
```

[figure not shown]
Note: SAPE denotes any dichotomous efficacy parameter, regionn and hscrpn are stratification factors, we can add other stratification when needed.

The supportive efficacy parameters utilizing the non-hs-CRP will be analyzed in a similar manner as their secondary efficacy counterparts using hs-CRP.

All analyses will be performed two-sided at the 5% significance level. No formal multiple comparison adjustment will be made; therefore, results should be interpreted with the multiplicity in mind. The estimated treatment effect (relative to placebo), e.g., odds ratio, from the model, along with a two-sided 95% confidence interval (CI) and p-value, will be tabulated where appropriate. The Newcombe's CI of the rate difference between JTE-051 dose and placebo will be computed when performing the Fisher's exact test. Graphical presentations of the treatment profile will be depicted for the primary and key secondary analyses. Sensitivity analysis and model fit assessment may be conducted, and data transformation may be employed if appropriate.

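### Moderate EULAR response is tested as an exclusive category, so its p-value and trend do not track benefit; good-or-moderate should be tested instead (minor)

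*SAP*

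**What the plan says.** SAP 5.2.2 and protocol 3.8.3.1 list two EULAR endpoints, both at Week 12. In the SAP they are "Percentage of subjects with good European League Against Rheumatism (EULAR) response at Week 12" and "Percentage of subjects with moderate EULAR response at Week 12". The protocol synopsis lists the same pair.

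The only definition is the three-by-three table in SAP 5.2.5.7, repeated in protocol Appendix 5. Its lead-in is "This parameter considers both the change in DAS28 between two time points, as well as DAS28 value at a specific time point". Each combination of present DAS28-CRP and improvement leads to exactly one of good, moderate or no response.

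For dichotomous secondary parameters SAP 6.4.2 prescribes "the Fisher's exact test for pairwise comparisons with placebo and the Cochran-Armitage test for trend", as does protocol 3.8.3.2. Neither makes an exception for the moderate category. SAP 6.4.3 adds: "All analyses will be performed two-sided at the 5% significance level". It continues: "No formal multiple comparison adjustment will be made; therefore, results should be interpreted with the multiplicity in mind".

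No visible text defines a combined good-or-moderate endpoint, an ordered analysis of the three categories, or how to read the direction of a moderate-only result.

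**The concern.** A binary endpoint suits a comparison with placebo, and above all a trend test over ordered doses, when more benefit can only push its rate one way. The moderate share lacks that property. It gains subjects who leave the no-response category and loses subjects who reach good response, and the test treats the best and the worst outcome as the same failure.

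The plan's other graded endpoints are cumulative: ACR20/50/70, DAS28-CRP below 3.2 and below 2.6, and the low-activity and remission cut-offs for SDAI and CDAI. A subject who reaches the better level still counts at the lesser one. Moderate EULAR response is the exception.

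The trial compares four doses with placebo without multiplicity adjustment, so its secondary results will be read largely as a pattern across doses and endpoints. A prespecified p-value and trend that can be flat or reversed for an effective dose muddies that pattern.

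**Working it through.** **Inputs.** From the documents: 50 subjects per group (SAP 6.1), two-sided Fisher test at 5% (SAP 6.4.2 and 6.4.3), exclusive categories (SAP 5.2.5.7). Expected EULAR rates are not given, so every rate below is an assumption. All 50 per arm are taken as evaluable. SAP 6.4.10 excludes subjects with missing data from by-visit analyses, so actual numbers may be smaller.

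**Step 1: check the method on the plan's own figure.** Power is the sum, over all x and y from 0 to n, of Bin(x; n, p0) × Bin(y; n, p1), taken where the two-sided Fisher p-value is at most 0.05. For ACR20 with a difference of 0.30 and placebo rates of 0.25, 0.35 and 0.45, the plan's 47, 48 and 47 per group each give 79.9%. With 50 per group the results are 83.5%, 82.8% and 83.5%. The plan's figure is reproduced.

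**Step 2: what each endpoint responds to.** Suppose that, relative to placebo, the drug moves a fraction a from none to moderate, b from moderate to good, and c from none to good, and worsens nobody. Then:

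- change in moderate = a − b
- change in good = b + c
- change in good-or-moderate = a + c

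Only the first contains a benefit with a minus sign. The other two can only rise with benefit, and between them they cover all three moves.

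**Step 3: exact Fisher power, 50 per arm.** Rates are good/moderate. For moderate alone, significance in favour of and against the drug is shown separately.

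| Placebo | Drug | Moderate: for / against | Good | Good-or-moderate |
|---|---|---|---|---|
| 10/35% | 35/35% | 1.5% / 1.5% | 82% | 67% |
| 15/30% | 35/40% | 13% / 0.1% | 57% | 84% |
| 15/35% | 45/30% | 0.4% / 5.1% | 89% | 67% |
| 15/40% | 45/25% | about 0% / 29% | 89% | 27% |
| 15/40% | 55/20% | about 0% / 52% | 99% | 48% |
| 10/40% | 40/10% | about 0% / 93% | 93% | 3.5% (1.8% each way) |
| 10/30% | 20/50% | 46% / about 0% | 19% | 83% |
| 5/25% | 15/50% | 67% / about 0% | 24% | 93% |

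As an example in counts out of 50, take placebo with 8 good and 20 moderate, and a dose with 28 good and 10 moderate. Moderate alone gives p = 0.049 in favour of placebo; good gives p = 0.00006.

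**Step 4: trend over five groups.** This used a simulated asymptotic Cochran-Armitage test, scores 1 to 5, 40,000 runs, with good response rising evenly from 15% to 45%. With moderate flat at 40%, its trend is significant 2.5% of the time in each direction. With moderate falling evenly from 40% to 25%, a significant downward trend appears 43% of the time. The upward trend in good is detected about 96% of the time in both cases.

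**Step 5: a smoother check.** In an assumed normal model for DAS28 (baseline mean 5.2, SD 0.9; improvement SD 1.2), mean improvements of 0.6, 1.5 and 2.8 give moderate rates of 32%, 40% and 26%, while good goes 15%, 34%, 70%. With baseline means of 5.7 and 6.2 the moderate rate also rises and then falls, but over the same range it stays above its placebo level. Across these runs moderate alone was significant against the drug at most 6.6% of the time.

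**The case against.** The strongest reply is that the plan loses little. Good response is already planned and has 57% to 99% power in the five scenarios with gains in good of 20 points or more and a fall in moderate of at most 20 points; in the first and third it beats good-or-moderate. The same DAS28-CRP data are also analysed as a continuous change and against two cut-offs. SAP 6.4.4 tabulates frequencies by treatment, so a reader can add good and moderate together. This is one unadjusted item in a long secondary list, and no decision rule rests on it. All of that stands and sets the severity.

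Four stronger readings are tempting, and the documents support none of them.

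- *That the plan would miss a EULAR benefit.* In the first scenario the good endpoint detects it 82% of the time.
- *That an effective dose would generally look harmful.* This needs a large net fall in the moderate share: 35% to 30% gives a significant result against the drug only 5.1% of the time, 40% to 25% gives 29%, and 40% to 20% about half. The plan gives no rates that would make such a fall expected.
- *That the moderate result cannot be interpreted at all.* If the drug mainly lifts non-responders into moderate, the endpoint points the right way, with 46% or 67% power in the last two rows. It is also readable beside the good rate.
- *That the combined endpoint would reveal a pure moderate-to-good shift.* It would not (3.5% power); that shift shows on good response, which is why both are needed.

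Visibility is a further limit. SAP numbering runs from 5.2.2 to 5.2.5 and from 6.4.4 to 6.4.7, and lines in its contents list are blacked out. A combined or ordered EULAR analysis may sit there. The sponsor may also intend at-least-moderate, but the visible text does not say so.

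**Conclusion.** The point holds as a minor one. By the plan's own table the moderate share counts good responders as failures, and it is nevertheless tested pairwise and for trend. Its rate is not monotone in benefit, so the tests can be uninformative (3% power where good has 82%) or point against an effective dose (29% where good has 89%). Even where moderate alone points the right way, good-or-moderate does better: 83% against 46%, and 93% against 67%. These sizes rest on assumed EULAR rates and 50 evaluable subjects per arm; the non-monotonicity itself follows from the table, whatever the rates. The primary ACR20 analysis and the sample size are not affected.

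**What to change.** In SAP 5.2.2, replace the tested moderate endpoint with good or moderate EULAR response at Week 12. Keep good response at Week 12 as the second dichotomy, and state that the moderate category alone is shown descriptively, without a p-value or trend test. Make the same change in protocol 3.8.3.1 and the synopsis for consistency at the next amendment; protocol 3.8 lets the SAP modify the plan, so the SAP wording can go first. If at-least-moderate was always meant, or a combined analysis already exists in a section not visible here, a clarifying line is enough.

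The cost is a line or two of wording and one derived variable. No new data are needed, and the sample size does not change.
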